5.2.4 Recommended Dose Modifications

Every effort should be made to administer the study drugs on the planned dose and schedule.

In the event of significant toxicity, dosing may be delayed and/or reduced as described below. Toxicity will be graded according to NCI CTCAE, version 4.03. In the event of multiple toxicities, dose modification should be based on the worst toxicity observed. Patients are to be instructed to notify Investigators at the first occurrence of any adverse symptom.

Dose modifications may occur:

- Within a cycle: dosing interruption until adequate recovery and dosing reduction, if required, during a given treatment cycle;
Between cycles: next cycle administration may be delayed due to persisting toxicity when a new cycle is due to start.

5.2.4.1 Dose Interruptions

Appropriate follow up assessments should be done until adequate recovery occurs as assessed by the Investigator. Criteria required before treatment can resume are described in section Dose Delays ([Section 5.2.4.2](#)).

Doses may be held as needed until toxicity resolution. Depending on when the AE resolved, a treatment interruption may lead to the patient missing all subsequent planned doses within that same cycle or even to delay the initiation of the subsequent cycle.

If the AE that led to the treatment interruption recovers within the same cycle, then redosing in that cycle is allowed. Doses omitted for toxicity are not replaced within the same cycle. The need for a dose reduction at the time of treatment resumption should be based on the criteria defined in Dose Modifications ([Section 5.2.4.3](#)), unless

expressly agreed otherwise following discussion between the Investigator and the MDACC IND Office.

In the event of a treatment interruption for reasons other than treatment-related toxicity (eg, elective surgery) lasting >28 days, treatment resumption will be decided in consultation with the MDACC IND Office.

5.2.4.2 Dose Delays

Patients experiencing Grade 3 or 4 potentially treatment related toxicity or intolerable Grade 2 toxicity despite supportive care should have their treatment interrupted/delayed. Appropriate follow-up assessments should be done until adequate recovery (or until deemed irreversible) occurs as assessed by the Investigator. A treatment delay of more than 4 weeks due to lack of recovery will result in discontinuation of the patient from the treatment, unless continuation (with dose reduction) upon subsequent recovery is considered in the patient's best interest by the investigator (eg, proven clinical benefit).

A new cycle of treatment (or Day 15 of any cycle subject to treatment) may begin only if:

- ANC >/= 1,000/ μ L;
- Platelet count >/= 50,000/ μ L;
- Hemoglobin >/= 8 g/dL;
- Non-hematologic toxicities have returned to baseline or Grade </=1 severity (or, at the investigator discretion, Grade </=2 if not considered a safety risk for the patient).

Withhold scheduled dose for grade >/=3 clinically significant lab abnormality attributed to the treatment. Resume the treatment once the lab abnormality returns to grade </=1. In cases of potential liver injury, consultation with a hepatologist should be considered in the decision to initiate treatment with anti-inflammatory medications.

If these conditions are not met, treatment must be delayed by 1 week. If, after a 1-week delay, all toxicities have recovered within the limits described above, treatment

with study drugs, can be resumed. Both study drugs should be delayed simultaneously if applicable. If the patient has not recovered after 1 week of delay, treatment may be delayed by 1 more week. However, initiation of the next cycle can only be delayed by a maximum of 4 weeks (28 days). Therefore, if persisting toxicity does not allow for the resumption of treatment, the patient will be permanently discontinued.

For all \geq Grade 3 hematological or non-hematological AEs that are NOT study drug-related, at the discretion of the treating physician, study drug dosing may be continued.

Elevation of amylase and/or lipase without clinical and/or radiographic evidence of pancreatitis are not considered DLT, and the patient can resume treatment at any grade at the discretion of the treating physician in consultation with the PI.

For Arm D, patients who experience:

- Grade 1 and 2 diarrhea related to radiation therapy and chemotherapy occurs in majority of patients starting around the end of the 3rd week of radiation therapy. Diarrhea prior to the 3rd week of radiation therapy is not usually associated with chemotherapy and radiation therapy and other causes need to be ruled out including C. Diff. This diarrhea lasts through the 5th week of radiation therapy and up to a week after the external beam radiation therapy is completed. This diarrhea is usually controlled with Imodium AD but sometimes Lomotil is used to control it. Grade 3 or higher diarrhea – not controlled with Imodium or Lomotil is rare – usually less than 2-3% in patients in patients receiving chemotherapy and radiation therapy.
- Grade 1 and 2 diarrhea related to radiation may continue avelumab or utomilumab (4-1BB) at the discretion of the physician,
- Grade 3 and 4 diarrhea related to radiation will hold avelumab or utomilumab (4-1BB). At the physician's discretion, avelumab or utomilumab (4-1BB) may continue at same dose if diarrhea improves to $</=$ Grade 1.
- In case the event of diarrhea is suspected to be immune-related and/or in the case the event of diarrhea does not respond to the measures applied for

radiotherapy-induced diarrhea and has an increase in severity, follow the toxicity management described for diarrhea/colitis in the immune-related adverse event toxicity management (Table 10).

Patients continuing on protocol after more than a 28 days delay in treatment can continue on a case by case basis after discussion with the Medical Monitor and at the discretion of the treating physician.

Each dose modification or treatment delay has to be documented in the eCRF, including the respective reason.

5.2.4.3 Dose Modifications

In the event that a DLT that is at least possibly related to one of the study drugs occurs, patients will halt treatment with study drugs until symptoms resolve to the grade outlined in [Section 5.2.4.2](#), and then treatment can be restarted. After the first two cycles reduction in the frequency of dosing in study drug(s) may be required based on the worst toxicity experienced in the previous cycle.

No specific dose adjustments are recommended for Grade 1/2 treatment-related toxicity. However, investigators should always manage their patients according to their medical judgment based on the particular clinical circumstances.

During dose escalation cohorts, patients experiencing recurrent and intolerable Grade 2 toxicity may resume dosing at the next lower dose level or at a decreased frequency once recovery to $>/=\text{Grade 1}$ or baseline is achieved. Patients enrolled in the expansion cohorts may resume dosing, once recovery to $</=\text{Grade 1}$ or baseline is achieved after experiencing recurrent and intolerable $>/=\text{Grade 2}$. If a dose or frequency reduction is required due to the treatment related toxicity, this may be allowed as an alternative to discontinuation of treatment, upon agreement with the MDACC IND Office.

Once a patient has a dose reduction or reduction in the frequency in the dosing for a drug-related toxicity, the dose will not be re-escalated. Patient requiring more than two dose reductions will be withdrawn from treatment unless otherwise agreed between the investigator and the MDACC IND Office.

Adverse events (both non-serious and serious) associated with study drug(s) exposure may represent an immunologic etiology. These adverse events may occur shortly after the first dose or several months after the last dose of treatment. Immunotherapy study drugs (avelumab, utomilumab, and PF-04518600) must be withheld for drug-related toxicities and severe or life-threatening AEs as per Table 8-10 below. Where appropriate, these guidelines include the use of oral or intravenous treatment with corticosteroids as well as additional anti-inflammatory agents if symptoms do not improve with administration of corticosteroids. Note that several courses of steroid tapering may be necessary as symptoms may worsen when the steroid dose is decreased. The dose modification guidelines are intended to be applied when the physician determines the events to be related to one or more of the immunotherapy study drugs (avelumab, utomilumab, and PF-04518600).

For subjects whose dose was withheld due to toxicity, subjects may resume immunotherapy study drug(s) (avelumab, utomilumab, and PF-04518600) upon resolution of toxicity to Grade 0-1 or baseline.

Table 8. Adverse Drug Reactions Requiring Immunotherapy Agent Discontinuation or Modification

In the following table, immunotherapy study drugs or agents refer to avelumab, utomilumab, or PF-04518600.

Any Grade 4 Adverse Drug Reactions (ADRs) require treatment discontinuation with immunotherapy agents (avelumab, utomilumab, or PF-04518600) except for single laboratory values out of normal range that are unlikely related to study treatment as assessed by the Investigator, do not have any clinical correlate, and resolve within 7 days with adequate medical management

Any Grade 3 ADRs require treatment discontinuation with immunotherapy agents except for any of the following:

- Transient (\leq 6 hours) Grade 3 flu-like symptoms or fever, which is controlled with medical management
- Transient (\leq 24 hours) Grade 3 fatigue, local reactions, headache, nausea, emesis that resolves to Grade \leq 1
- Single laboratory values out of normal range (excluding Grade \geq 3 liver function test increase) that are unlikely related to study treatment according to the Investigator, do not have any clinical correlate, and resolve to Grade \leq 1 within 7 days with adequate medical management
- Tumor flare phenomenon defined as local pain, irritation, or rash localized at sites of known or suspected tumor
- Change in ECOG PS to \geq 3 that does not resolve to \leq 2 within 14 days (infusions should not be given on the following cycle, if the ECOG PS is \geq 3 on the day of study drug administration)

Any Grade 2 ADR should be managed as follows:

- If a Grade 2 ADR resolves to Grade \leq 1 by the last day of the current cycle, treatment may continue.
- If a Grade 2 ADR does not resolve to Grade \leq 1 by the last day of the current cycle, infusions should not be given on the following cycle. If at the end of the following cycle the event has not resolved to Grade 1, the subject should permanently discontinue treatment with an **immunotherapy agent** ADR (except for hormone insufficiencies, that can be managed by replacement therapy; for these hormone insufficiencies, up to 2 subsequent doses may be omitted).
- Upon the second occurrence of the same Grade 2 ADR (except for hormone insufficiencies that can be managed by replacement therapy) in the same subject, treatment with **immunotherapy agents** has to be permanently discontinued.

Table 9. Treatment Modification for Symptoms of Infusion-Related Reactions

In the following table, immunotherapy study drugs or agents refer to avelumab, utomilumab, or PF-04518600.

NCI-CTCAE Grade	Treatment Modification for Study Drug
Grade 1 – mild Mild transient reaction; infusion interruption not indicated; intervention not indicated.	Decrease the study drug infusion rate by 50% and monitor closely for any worsening. The total infusion time for study drug should not exceed 120 minutes.
Grade 2 – moderate Therapy or infusion interruption indicated but responds promptly to symptomatic treatment (for example, antihistamines, NSAIDs, narcotics, IV fluids); prophylactic medications indicated for ≤ 24 h.	Stop study drug infusion. Resume infusion at 50% of previous rate once infusion-related reaction has resolved or decreased to at least Grade 1 in severity, and monitor closely for any worsening.
Grade 3 or Grade 4 – severe or life-threatening Grade 3: Prolonged (for example, not rapidly responsive to symptomatic medication and/or brief interruption of infusion); recurrence of symptoms following initial improvement; hospitalization indicated for clinical sequelae. Grade 4: Life-threatening consequences; urgent intervention indicated.	Stop the study drug infusion immediately and disconnect infusion tubing from the subject. Subjects have to be withdrawn immediately from study drug treatment and must not receive any further study drug treatment.

 - Once the immunotherapy agents infusion rate has been decreased by 50% or interrupted due to an infusion-related reaction, it must remain decreased for all subsequent infusions. - If the subject has a second infusion-related reaction Grade ≥ 2 on the slower infusion rate, the infusion should be stopped and the subject should be removed from study treatment. - If hypersensitivity reaction occurs, the subject must be treated according to the best available medical practice. 	

IV = intravenous; NCI-CTCAE = National Cancer Institute-Common Terminology Criteria for Adverse Event; NSAIDs = nonsteroidal anti-inflammatory drugs.

Table 10. Management of Immune-mediated Adverse Reactions

In the following table, immunotherapy study drugs or agents refer to avelumab, utomilumab, or PF-04518600.

Since inhibition of PD-L1 stimulates the immune system, immune-related AEs (irAEs) may occur.

Treatment of irAEs is mainly dependent upon severity (NCI-CTCAE grade):

Grade 1 to 2: treat symptomatically or with moderate dose steroids, more frequent monitoring

Grade 1 to 2 (persistent): manage similar to high grade AE (Grade 3 to 4)

Grade 3 to 4: treat with high dose corticosteroids

Treatment of gastrointestinal, dermatological, pulmonary, hepatic and endocrine irAEs should follow guidelines set forth in the table.

Gastrointestinal irAEs		
Severity of Diarrhea / Colitis (NCI-CTCAE v4.03)	Management	Follow-up
Grade 1 Diarrhea: < 4 stools/day over Baseline Colitis: asymptomatic	Continue immunotherapy agent therapy Symptomatic treatment (for example, loperamide)	Close monitoring for worsening symptoms Educate subject to report worsening immediately If worsens: Treat as Grade 2 or 3/4
Grade 2 Diarrhea: 4 to 6 stools per day over Baseline; IV fluids indicated < 24 hours; not interfering with ADL Colitis: abdominal pain; blood in stool	Delay immunotherapy agent therapy Symptomatic treatment	If improves to Grade 1: Resume immunotherapy agent therapy If persists > 5 to 7 days or recur: 0.5 to 1.0 mg/kg/day methylprednisolone or equivalent When symptoms improve to Grade 1, taper steroids over at least 1 month, consider prophylactic antibiotics for opportunistic infections, and resume immunotherapy agent therapy per protocol. If worsens or persists > 3 to 5 days with oral steroids: Treat as Grade 3 to 4
Grade 3 to 4 Diarrhea (Grade 3): ≥ 7 stools per day over Baseline; incontinence; IV fluids ≥ 24 hrs.; interfering with ADL Colitis (Grade 3): severe abdominal pain, medical intervention indicated, peritoneal signs Grade 4: life-threatening, perforation	Discontinue immunotherapy agent therapy per protocol 1.0 to 2.0 mg/kg/day methylprednisolone IV or equivalent Add prophylactic antibiotics for opportunistic infections Consider lower endoscopy	If improves: Continue steroids until Grade 1, then taper over at least 1 month If persists > 3 to 5 days, or recurs after improvement: Add infliximab 5 mg/kg (if no contraindication). Note: Infliximab should not be used in cases of perforation or sepsis

Dermatological irAEs		
Grade of Rash (NCI-CTCAE v4)	Management	Follow-up
Grade 1 to 2 Covering \leq 30% body surface area	Symptomatic therapy (for example, antihistamines, topical steroids) Continue immunotherapy agent therapy	If persists $>$ 1 to 2 weeks or recurs: Consider skin biopsy Delay immunotherapy agent therapy Consider 0.5 to 1.0 mg/kg/day methylprednisolone IV or oral equivalent. Once improving, taper steroids over at least 1 month, consider prophylactic antibiotics for opportunistic infections, and resume immunotherapy agent therapy If worsens: Treat as Grade 3 to 4
Grade 3 to 4 Covering $>$ 30% body surface area; life threatening consequences	Delay or discontinue immunotherapy agent therapy Consider skin biopsy Dermatology consult 1.0 to 2.0 mg/kg/day methylprednisolone IV or IV equivalent	If improves to Grade 1: Taper steroids over at least 1 month and add prophylactic antibiotics for opportunistic infections Resume immunotherapy agent therapy
Pulmonary irAEs		
Grade of Pneumonitis (NCI-CTCAE v4)	Management	Follow-up
Grade 1 Radiographic changes only	Consider delay of immunotherapy agent therapy Monitor for symptoms every 2 to 3 days Consider Pulmonary and Infectious Disease consults	Re-image at least every 3 weeks If worsens: Treat as Grade 2 or Grade 3 to 4
Grade 2 Mild to moderate new symptoms	Delay immunotherapy agent therapy Pulmonary and Infectious Disease consults Monitor symptoms daily, consider hospitalization 1.0 mg/kg/day methylprednisolone IV or oral equivalent Consider bronchoscopy, lung biopsy	Re-image every 1 to 3 days If improves: When symptoms return to near Baseline, taper steroids over at least 1 month and then resume immunotherapy agent therapy and consider prophylactic antibiotics If not improving after 2 weeks or worsening: Treat as Grade 3 to 4
Grade 3 to 4 Severe new symptoms; New / worsening hypoxia; life-threatening	Discontinue immunotherapy agent therapy Hospitalize	If improves to Baseline: Taper steroids over at least 6 weeks If not improving after 48 hours or worsening:

	
Pulmonary and Infectious Disease consults 2 to 4 mg/kg/day methylprednisolone IV or IV equivalent Add prophylactic antibiotics for opportunistic infections Consider bronchoscopy, lung biopsy
	Add additional immunosuppression (for example, infliximab, cyclophosphamide, IV immunoglobulin, or mycophenolate mofetil)
--	---	---

Hepatic irAEs

Grade of Liver Test Elevation (NCI-CTCAE v4)	Management	Follow-up
Grade 1 Grade 1 AST or ALT > ULN to 3.0 x ULN and / or total bilirubin > ULN to 1.5 x ULN	Continue immunotherapy agent therapy	Continue liver function monitoring If worsens: Treat as Grade 2 or 3 to 4
Grade 2 AST or ALT > 3.0 to \leq 5 x ULN and / or total bilirubin > 1.5 to \leq 3 x ULN	Delay immunotherapy agent therapy Increase frequency of monitoring to every 3 days	If returns to Baseline: Resume routine monitoring, resume immunotherapy agent therapy If elevations persist > 5 to 7 days or worsen: 0.5 to 1 mg/kg/day methylprednisolone or oral equivalent and when LFT returns to Grade 1 or Baseline, taper steroids over at least 1 month, consider prophylactic antibiotics for opportunistic infections, and resume immunotherapy agent therapy
Grade 3 to 4 AST or ALT > 5 x ULN and / or total bilirubin > 3 x ULN	Discontinue immunotherapy agent therapy Increase frequency of monitoring to every 1 to 2 days 1.0 to 2.0 mg/kg/day methylprednisolone IV or IV equivalent Add prophylactic antibiotics for opportunistic infections Consult gastroenterologist Consider obtaining MRI/CT scan of liver and liver biopsy if clinically warranted	If returns to Grade 2: Taper steroids over at least 1 month If does not improve in > 3 to 5 days, worsens or rebounds: Add mycophenolate mofetil 1 gram (g) twice daily If no response within an additional 3 to 5 days, consider other immunosuppressants per local guidelines

Endocrine irAEs

Endocrine Disorder	Management	Follow-up
Asymptomatic TSH abnormality	Continue immunotherapy agent therapy	

	If TSH < 0.5 x LLN, or TSH > 2 x ULN, or consistently out of range in 2 subsequent measurements: include T4 at subsequent cycles as clinically indicated; consider endocrinology consult	
Symptomatic endocrinopathy	Evaluate endocrine function Consider pituitary scan Symptomatic with abnormal lab / pituitary scan: Delay immunotherapy agent therapy 1 to 2 mg/kg/day methylprednisolone IV or by mouth equivalent Initiate appropriate hormone therapy No abnormal lab / pituitary MRI scan but symptoms persist: Repeat labs in 1 to 3 weeks / MRI in 1 month	If improves (with or without hormone replacement): Taper steroids over at least 1 month and consider prophylactic antibiotics for opportunistic infections Resume immunotherapy agent therapy Subjects with adrenal insufficiency may need to continue steroids with mineralocorticoid component
Suspicion of adrenal crisis (for example, severe dehydration, hypotension, shock out of proportion to current illness)	Delay or discontinue immunotherapy agent therapy Rule out sepsis Stress dose of IV steroids with mineralocorticoid activity IV fluids Consult endocrinologist If adrenal crisis ruled out, then treat as above for symptomatic endocrinopathy	
Cardiac irAEs		
Myocarditis	Management	Follow-up
New onset of cardiac signs or symptoms and / or new laboratory cardiac biomarker elevations (e.g. troponin, CK-MB, BNP) or cardiac imaging abnormalities suggestive of myocarditis.	Withhold immunotherapy agent therapy Hospitalize. In the presence of life threatening cardiac decompensation, consider transfer to a facility experienced in advanced heart failure and arrhythmia management. Cardiology consult to establish etiology and rule-out immune-mediated myocarditis. Guideline based supportive treatment as appropriate per cardiology consult.* Consider myocardial biopsy if recommended per cardiology consult.	If symptoms improve and immune-mediated etiology is ruled out, re-start immunotherapy agent therapy. If symptoms do not improve/worsen, viral myocarditis is excluded, and immune-mediated etiology is suspected or confirmed following cardiology consult, manage as immune-mediated myocarditis.
Immune-mediated myocarditis	Permanently discontinue immunotherapy agent . Guideline based supportive treatment as appropriate per cardiology consult.* Methylprednisolone 1-2 mg/kg/day.	Once improving, taper steroids over at least 1 month and add prophylactic antibiotics for opportunistic infections. If no improvement or worsening, consider additional immunosuppressions (e.g. azathioprine, cyclosporine A)

ADL = activities of daily living; ALT = alanine aminotransferase; AST = aspartate aminotransferase; CT = computed tomography; irAE = immune-related adverse event; IV=intravenous; LFT = liver function test; LLN = lower limit of normal; MRI = magnetic resonance imaging; NCI-CTCAE = National Cancer Institute-Common Terminology Criteria for Adverse Event; T4 = free thyroxine; TSH = thyroid-stimulating hormone; ULN = upper limit of normal.

*Local guidelines, or eg. ESC or AHA guidelines

ESC guidelines website:

<https://www.escardio.org/Guidelines/Clinical-Practice-Guidelines>

AHA guidelines website:

<http://professional.heart.org/professional/GuidelinesStatements/searchresults.jsp?q=&y=&t=1001>

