3.2.4 Arm D: Avelumab + Utomilumab (4-1BB) + Radiation

In the dose escalation phase, the dose of radiation will be de-escalated in combination with fixed doses of utomilumab (4-1BB) and avelumab to evaluate the safety, tolerability, and MTD in patients with advanced solid tumors.

Once the MTD or RP2D is determined, the Arm D MTD expansion will enroll up to 14 patients at the previously established safe dose for additional safety and correlative studies to establish the RP2D for this combination.

Radiation will be administered to 1-3 metastatic sites. This will be de-escalated from a total of 24 Gy to 21 Gy. The technique will be stereotactic radiation via intensity-modulated radiation therapy (IMRT) or Volumetric modulated arc therapy (VMAT). The radiation lead-in will occur within Days -5 to -1 with a +/- 3 day window. There will be 3 fractions or days of radiation. In all cases, the radiation must initiate and end within the radiation lead-time. Cycle 1 Day 1 study drug treatment should begin within 3 days of last dose of radiation.

Utomilumab (4-1BB) will be administered at the fixed flat dose of 100 mg IV on Day 1 of each 28-day cycle or every 4 weeks. Avelumab will be administered at the fixed dose of 10 mg/kg IV on Day 15 of Cycle 1 and Days 1 and 15 of each subsequent 28-day cycle or every 2 weeks. Premedications will be administered per institutional standard.

On days when both avelumab and utomilumab are administered, avelumab will be administered first.

Patients will be restaged at the end of every two cycles and tumor response evaluation will be based on RECIST 1.1 and irRECIST. Patients may be allowed to continue treatment after two cycles of avelumab combinations if there is continued clinical response or disease stabilization and patients do not have significant toxicities. Following radiation, a patient may continue treatment on this combination therapy until the patient experiences confirmed disease progression, unacceptable adverse event(s), intercurrent illness that prevents further administration of treatment, and/or treatment is discontinued following investigator's decision to withdraw the patient, pregnancy, patient withdraws consent, noncompliance with trial treatment or procedure requirements, or administrative reasons.

Table 6: Dosing for Arm D: Avelumab + Utomilumab (4-1BB) + Radiation

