Dose Level	Radiation Days -5 to -1	Utomilumab (4-1BB) IV Every 4 Weeks Starting Cycle 1 Day 1	Avelumab IV Every 2 Weeks Starting Cycle 1 Day 15
1 (Start)	24 Gy in 8 Gy / fraction for 3 fractions	100 mg	10 mg/kg
-1	21 Gy in 7 Gy/ fraction for 3 fractions	100 mg	10 mg/kg

As of Amendment Version 09, the avelumab and radiation dosing for Arm D was revised; therefore, the dose de-escalation was re-started.

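### Section 5.2.4.3 prints the restart threshold for dose-escalation cohorts with the inequality reversed, so the unresolved Grade 2 toxicity that triggers the rule already satisfies it

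*Combined protocol and SAP*

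**What the plan says.** The sentence at issue, in Section 5.2.4.3 of the protocol, says that patients in dose-escalation cohorts with "recurrent and intolerable Grade 2 toxicity may resume dosing at the next lower dose level or at a decreased frequency once recovery to" a stated grade. The threshold itself is printed as "at a decreased frequency once recovery to $>/=\text{Grade 1}$ or baseline is achieved".

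The other restart rules that bear on the same situation are these:

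- **Section 5.2.4.3, next sentence.** "Patients enrolled in the expansion cohorts may resume dosing, once recovery to" Grade 1 or lower, or baseline.
- **Section 5.2.4.2.** Intolerable Grade 2 toxicity despite supportive care should lead to a hold. A new cycle, or a Day 15 dose, may start only if "Non-hematologic toxicities have returned to baseline or Grade </=1 severity (or, at the investigator discretion, Grade </=2 if not considered a safety risk" to the patient.
- **Section 5.2.4.3, text before Table 8.** Withheld immunotherapy may resume "upon resolution of toxicity to Grade 0-1 or baseline".
- **Table 8.** A Grade 2 reaction not down to Grade 1 or lower by the end of the cycle means no infusions in the following cycle. "Upon the second occurrence of the same Grade 2 ADR", immunotherapy must stop permanently, except for hormone insufficiencies that replacement therapy can manage.

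On whether the rule still applies, Section 3.2.4 says of Arm D: "In the dose escalation phase, the dose of radiation will be de-escalated in combination with fixed doses of" utomilumab and avelumab. It adds that, as of Version 09, "the avelumab and radiation dosing for Arm D was revised; therefore, the dose de-escalation was re-started". Table 12 also lists Arm D's 12 patients in its dose-escalation column.

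**The concern.** A restart rule should say how far a toxicity must fall before the patient is dosed again. This one sets a floor instead of a ceiling. A patient held for Grade 2 toxicity meets the printed criterion on the day of the hold. A patient who recovers fully to Grade 0 meets it only through the baseline alternative.

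This is an operative re-dosing threshold in the dose-finding part of a combination trial. A reader who follows the sentence alone could restart at unresolved Grade 2. That would skip the judgment, required by Section 5.2.4.2, that the residual toxicity is not a safety risk. The protocol gives no reason for a looser threshold in dose finding than in expansion.

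Two smaller defects sit in the same sentence. It lets recurrent Grade 2 toxicity resume where Table 8 can require permanent discontinuation. And for Arm D, a lower dose level offers nothing to reduce.

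**Working it through.** The plan states no figure to reproduce. The check is which grades satisfy each rule.

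**Step 1: the threshold.** The rule is triggered at Grade 2, so at the restart decision the toxicity can be at Grade 0, 1 or 2 if it has not worsened.

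| Grade at decision | Dose-escalation sentence as printed (≥ 1) | Expansion sentence (≤ 1) |
|---|---|---|
| 0 | no (passes only via baseline) | yes |
| 1 | yes | yes |
| 2 | yes | no |

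The baseline alternative is the same in both sentences and does not affect the comparison. The two rules agree at Grade 1. The sign decides whether unresolved Grade 2 passes. Read literally, the printed sign would also admit Grades 3 and 4, but Table 8 governs those separately.

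**Step 2: comparison with the other rules.** Section 5.2.4.2 admits Grades 0 and 1 by default, and Grade 2 only by investigator discretion when it is not a safety risk. The resumption text before Table 8 admits Grades 0 and 1. Table 8 requires Grade 1 or lower for infusions to go on into the following cycle. All are upper bounds. The dose-escalation sentence alone is a lower bound, and it carries no safety-risk condition.

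**Step 3: recurrence.** The sentence permits restart after recurrent Grade 2 toxicity. Table 8 requires permanent discontinuation when the same Grade 2 reaction occurs a second time (hormone insufficiencies excepted). Correcting the sign does not remove this conflict. The expansion sentence shares it.

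**Step 4: dose level in Arm D.** Table 6 gives utomilumab 100 mg and avelumab 10 mg/kg at both levels. Only radiation differs: 24 Gy at level 1 and 21 Gy at level -1. Radiation is finished before Cycle 1 Day 1, so moving down a level changes nothing still to be given. Decreased frequency remains usable.

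**Step 5: exposure.** Section 3.5 requires six patients before a level is declared the MTD, and Section 9.3 plans two levels of up to six.

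- Level 1 declared the MTD: 1 × 6 = 6 planned patients.
- Level -1 also used: at most 2 × 6 = 12 planned patients.

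Only those with recurrent, intolerable Grade 2 toxicity come under the rule, and the documents give no incidence for that. Replacement of non-evaluable patients (Sections 3.3 and 9.1) could raise the numbers treated slightly.

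**The case against.** The strongest case is that this is a slip whose meaning is recoverable and whose harm is already blocked.

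**Intent.** The sentence speaks of recovery, and unresolved Grade 2 is not recovery. Table 9, on infusion reactions, uses the words at least before Grade 1 to mean Grade 1 or better, so the sign may be shorthand for the same idea. This stands as an explanation. It does not make the printed threshold right: staff applying a safety rule should not have to infer the direction of its inequality.

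**Other rules.** The sentence is permissive, while Section 5.2.4.2 states a condition that must be met and Section 5.2.4.3 requires withholding under Tables 8 to 10. A restart that satisfied all of them would be safe. This stands and limits the consequence. The contradiction remains, and Section 5.2.4.2 itself allows Grade 2 at discretion, so the conflict there is with its default and its safety-risk condition.

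**Table 8 empties the rule.** If Table 8 prevails, a repeat of the same Grade 2 drug reaction never reaches a restart decision. What is left is, for example, hormone insufficiencies and events not judged drug-related. This is fair and narrows the exposure further. But nothing in the sentence says that Table 8 prevails.

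**Legacy wording.** Elsewhere the protocol separates the earlier Arm C escalation cohorts from the Arm D de-escalation, so the sentence could be a leftover. Section 3.2.4 and Table 12 point the other way, and their wording brings Arm D under the rule.

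**Text conversion.** A misread symbol in the text taken from the PDF cannot be fully excluded. It is unlikely, because the other signs in the same paragraph appear in the same format and make sense.

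**Conclusion.** The concern holds. The restart threshold in the dose-escalation sentence of Section 5.2.4.3 is wrong as written. It admits the unresolved Grade 2 toxicity that triggers it and contradicts the other restart rules. Most likely it is a drafting slip, but it sits in a safety rule and should be corrected.

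The consequence is limited. The rule reaches a subset of 6 to 12 planned Arm D de-escalation patients, of unknown size, and fewer still if Table 8 is taken to prevail. Grade 3 and 4 drug reactions are handled by Table 8. Nothing here bears on DLT counts, sample size or analysis.

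The conclusion assumes that the sign in the PDF is as read, that Arm D de-escalation counts as a dose-escalation cohort, and that no one from earlier escalation cohorts is still on treatment. The documents do not settle the last point. The conflict over recurrence is a separate contradiction. The dose-level point for Arm D is minor and creates no risk.

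**What to change.** 1. In the dose-escalation sentence of Section 5.2.4.3, change the threshold to Grade 1 or lower, or baseline.
2. Make the sentence subject to Table 8, so that a repeat of the same Grade 2 reaction leads to permanent discontinuation, hormone insufficiencies excepted. The expansion sentence has the same gap and should sensibly take the same cross-reference.
3. Optionally, for Arm D, delete the lower-dose-level option and keep decreased frequency.

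The discretion in Section 5.2.4.2 can stay as it is. The cost is one edited sentence, or two with the expansion cross-reference, and no change to design, sample size or analysis.
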